### 13.3 Sample Size

The sample size (N=90) is based on goals of estimating retention, recruitment, adherence and accrual rates and effect sizes to inform design of a larger efficacy trial. If the drop-out rate is  $>30\%$ , a larger study may not be feasible. With N=90, we are confident that this rate will be  $\leq 30\%$  when the observed drop-out rate is as large as 22% (upper limit of the one-sided 95% CI is 29.2%). Similarly, the lower limit of a one-sided 95% confidence interval for the recruitment rate can be estimated within 8.2% of the observed rate if we approach at least 100 participants to recruit 90, and the lower limit of a one-sided 95% confidence interval for the adherence can be estimated within 8.7% of the observed rate with N=90. Using the normal approximation to the Poisson, we can estimate the lower limit of the one-sided 95% confidence interval of the accrual rate within approximately 2 people per month if the observed rate is 11 people per month. To compare differences between the groups on changes in the PHQ-9 and GAD-7 scores, we can estimate the intervention effect within  $\pm 0.46$  SD with a sample size of 36/group (stepped-care telehealth, enhanced usual care), allowing 20% dropout of the 45/group randomized. This corresponds to 2.7 points on PHQ-9 and 1.9 points on GAD-7 using SDs from studies of change in the measures of 5.8 and 4.2 points, respectively.

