### 13.5 Secondary Objectives, Endpoints, Analysis Plans

For Objective 1.2.1, baseline descriptive statistics will be compared by intervention arm using chi-square tests for categorical variables and ANOVA for continuous variables. Due to randomization, we do not anticipate differences by intervention arm; if they are found, we will adjust for them in the analyses for Objectives 1.2.1, 1.2.2, 1.2.3, and 1.2.4. The Working Alliance Inventory will be summarized using descriptive statistics.

Depression and anxiety outcomes (PHQ-9 and GAD-7) will be analyzed using mixed-model analysis of covariance (ANCOVA) to account for intra-individual correlations among longitudinal measures. The model will contain terms for the intervention group, baseline value of the outcome, therapist or site staff person completing check-in calls, psychotropic medications use, a time effect (mid-, post-intervention), and the time by intervention interaction term (to test whether the intervention effects vary by time). Because participants may exhibit moderate or severe levels of either depression or anxiety, we will create a combined variable that indicates if a participant had moderate/severe depression or anxiety at mid- or post-intervention. Each stepped-care telehealth group will be compared with EUC using a GEE approach with a logit link to determine if rates of the combined outcome differ at mid- or post-intervention. Other outcome measures (sleep disturbance, fatigue, fear of recurrence, cancer-related distress, and quality of life) will be analyzed using ANCOVA at week 13 to meet objective 1.2.2.

For Objective 1.2.3, we will calculate total cost of the stepped-care telehealth (low intensity, high intensity) and the EUC interventions and average cost/survivor screened and randomized to each trial arm. Total cost includes costs of intervention implementation and health care costs for each participant.

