### **13.7 Reporting and Exclusions**

Unless we receive written or verbal withdrawal of consent, we will try to reach every participant for telephone calls, telephone sessions, and assessments as outlined in the protocol.

The dataset used in the analysis of Objective 1.1.1 will include all eligible participants to calculate recruitment rates. Accrual, retention, and adherence will be calculated on the participants who consent to participate in the study. The analysis of the secondary objectives and exploratory objective will include all participants who consent to participate in the study. The ANOVA models used for the secondary objectives use data from all available time points and allows for data to be missing at random. For the analyses of the secondary objectives and the exploratory objective, we will use an intent-to-treat approach. If participants are moved from low intensity to high intensity they will be analyzed using the

low intensity assignment (intent to treat). In exploratory models, we will analyze the impact of adherence by including it as a predictor.

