### **13.8 Evaluation of Response**

All participants in the study who complete the PHQ-9 and GAD-7 at Week 13 will be evaluable for response to the intervention. In sensitivity analyses, we will evaluate how imputation of these values utilizing either baseline or Week 7 data impact study conclusions. Note that this is a feasibility study and analyses of the intervention effects will be used to plan future studies, not to demonstrate efficacy.

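### The GEE for the combined depression/anxiety outcome has no stated missing-data method, and on observed visits alone it is biased if score-related drop-out differs by arm

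*Combined protocol and SAP*

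**What the plan says.** Section 13.5 sets out two analyses under Objective 1.2.1.

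- **PHQ-9 and GAD-7 scores:** a mixed-model ANCOVA with its terms listed: "The model will contain terms for the intervention group, baseline value of the outcome", followed by therapist or caller, psychotropic medication, time, and time by intervention.
- **Combined binary outcome:** "we will create a combined variable that indicates if a participant had moderate/severe depression or anxiety at mid- or post-intervention". Then: "Each stepped-care telehealth group will be compared with EUC using a GEE approach with a logit link". No terms, working correlation, weights or imputation are listed for this model.

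Three other statements bear on it:

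- On baseline differences between arms, 13.5 says: "if they are found, we will adjust for them in the analyses for Objectives 1.2.1, 1.2.2, 1.2.3, and 1.2.4".
- Section 13.7 says: "The ANOVA models used for the secondary objectives use data from all available time points and allows for data to be missing at random". It makes no matching statement for the GEE.
- Section 13.8 says: "All participants in the study who complete the PHQ-9 and GAD-7 at Week 13 will be evaluable for response to the intervention". It adds sensitivity analyses that impute missing Week 13 values from baseline or from Week 7.

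Section 13.3 plans for drop-out: "allowing 20% dropout of the 45/group randomized", which leaves 36 per group.

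**The concern.** A likelihood-based mixed model can use the baseline and Week 7 scores of someone who later drops out, so it tolerates drop-out that depends on those scores. An unweighted GEE on observed visits generally does not. It needs drop-out to be unrelated to earlier scores, given whatever is in the model.

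Here earlier scores have few ways in. Inclusion criterion 4.1.2 (GAD-7 of at least 10 and/or PHQ-9 of at least 8) uses the same cut-points that define moderate symptoms in 7.3.4, so the combined variable equals 1 for every participant at baseline and carries no information. Unless the model is extended, a participant lost before Week 7 contributes nothing. One lost after Week 7 helps the Week 13 estimate only through a dichotomised Week 7 value, and only under a working correlation other than independence.

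Different mechanisms by arm are plausible from the protocol itself. Stepped-care participants get weekly or biweekly calls while EUC participants get letters (4.4), and therapists pursue missed sessions (5.5). Improved stepped-care participants may stop while unimproved EUC participants lose interest, or the reverse. The odds ratio could then disagree with the mixed-model result on the same people for a purely technical reason, and the rates passed to the larger trial would be off.

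**Working it through.** **1. The plan's own figures.** 45 × 0.8 = 36 per group. Half-width = 1.96 × √(2/36) = 0.462 SD; × 5.8 = 2.68 PHQ-9 points; × 4.2 = 1.94 GAD-7 points. These match 13.3 (0.46 SD, 2.7 and 1.9 points). They are precision figures for score changes; the plan gives none for the combined outcome.

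**2. Assumptions for the check (not in the documents).** Week 13 rates of 60% in EUC and 42% in stepped care, from an assumed shift of 0.46 SD. This has the same size as the plan's half-width, but the plan does not state it as an effect. Correlations between visits 0.5 to 0.65. Drop-out 20-23% by Week 13, half before Week 7 depending on baseline and half after depending on the Week 7 score, with log-odds slopes of 0.4 to 0.7 per SD. Two pooled arms, 60,000 per arm; GEE with arm, time and arm by time.

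True log odds ratio from the rates: ln(0.42/0.58) − ln(0.60/0.40) = −0.323 − 0.405 = −0.73.

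**3. Week 13 log odds ratio.** A positive slope means higher scorers leave.

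| Slopes (EUC, stepped care) | True | GEE, independence | GEE, exchangeable | Imputation from baseline and Week 7 scores |
|---|---|---|---|---|
| 0.7, −0.7 | −0.73 | −0.44 | −0.55 | −0.72 |
| 0.4, −0.4 | −0.73 | −0.58 | −0.64 | −0.73 |
| 0, 0.7 | −0.73 | −0.87 | −0.82 | −0.73 |
| 0, −0.7 | −0.73 | −0.58 | −0.64 | −0.72 |
| 0.7, 0 | −0.75 | −0.61 | −0.66 | −0.75 |
| 0.7, 0.7 | −0.73 | −0.74 | −0.73 | −0.72 |

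The largest bias is (0.73 − 0.44)/0.73 = 40%. The smallest when mechanisms differ is (0.82 − 0.73)/0.73 = 12%. With equal mechanisms it is about 1%. Another simulation under similar assumptions gave −0.60 to −1.02 against −0.73, so exaggeration can also reach (1.02 − 0.73)/0.73 = 40%.

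**4. Check on the score scale.** PHQ-9 and GAD-7 were simulated directly, the outcome was cut at 8 and 10, drop-out was 20% per arm, and EUC rates ran from 30% to 79%. Bias in the Week 13 risk difference:

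- Score-related drop-out in stepped care only: −1.7 to −3.6 percentage points (independence), −1.1 to −1.9 (exchangeable).
- Opposite relations by arm: −4.7 to −6.9 and −2.3 to −3.3.
- Same relation in both arms: about 0 with no effect, up to about 1.2 with a 2.7-point effect.

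**5. Do the existing provisions cure it?**

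- *Baseline term alone.* With drop-out tied to Week 7 scores in stepped care only, and a full-data risk difference of −0.004, the estimates were −0.028 (independence), −0.016 (exchangeable), −0.010 (exchangeable plus baseline) and −0.003 (standardised on baseline and Week 7 scores). A baseline term suffices only when drop-out depends on baseline.
- *Carrying baseline forward.* Every drop-out becomes an event. With 20% completely random drop-out: EUC 0.8 × 0.60 + 0.2 = 0.68; stepped care 0.8 × 0.42 + 0.2 = 0.536. Log odds ratio = ln(0.536/0.464) − ln(0.68/0.32) = 0.144 − 0.754 = −0.61, which is 16% too small although nothing about the drop-out was informative.
- *Carrying Week 7 forward.* Bias of about 0 to +4 points with no effect, and up to about +6 with an effect.

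**6. Sampling error.** SE of the log odds ratio at 36 per group = √[1/(36 × 0.60 × 0.40) + 1/(36 × 0.42 × 0.58)] = √(0.1157 + 0.1140) = 0.48. At 20 and 16 per arm within strata it is 0.64 and 0.72. The half-width of a risk difference at a rate of 50% and 36 per group is 1.96 × √(2 × 0.25/36) = 23 points.

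**The case against.** Several points on the other side stand.

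- **Silence is not a decision.** A reader might infer that the plan chose an available-case GEE with no baseline term. Section 13.5 says neither; it leaves the model's terms and missing-data handling open, and it provides for baseline adjustment if the arms differ.
- **No stated assumption is contradicted.** A reader might infer that the plan assumes missing at random throughout and then breaks that assumption. Section 13.7 makes the statement for the ANOVA models only.
- **Missing scores are not ignored.** Section 13.8 plans imputation of the very scores that define the outcome.
- **The bias is small against the noise.** In the table it is at most 0.29 on the log odds scale, against an SE of 0.48. Section 13.8 also says the effect analyses serve planning, not proof of efficacy.
- **The sizes rest on assumptions.** The 40% needs opposite mechanisms and an independence structure. The first simulation pooled the strata and did not truncate baseline at the eligibility cut-points.

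What does not stand is the inference that the existing provisions are enough. The conditional adjustment is triggered by baseline imbalance, not by missingness, and it brings in no Week 7 scores. Both single imputations in 13.8 are biased themselves. Sampling error shrinks with sample size and this bias does not, and planning uses point estimates.

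**Conclusion.** The point holds as an unspecified method whose plain reading is not valid under score-related drop-out. It does not hold as a contradiction in the plan or as a proven distortion of results. If the relation between scores and drop-out differs by arm, the Week 13 log odds ratio is off by roughly 12-40% in either direction, depending on mechanism and working correlation, under the assumed 60% and 42% rates and 20-23% drop-out. If the relation is the same in both arms, the bias is near zero. It stays below the sampling error at 36 per group, so it would rarely change a conclusion in this trial; it matters for the estimates carried into the larger one. For a secondary outcome in a feasibility study this is a change worth making, not a threat to the primary objective.

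It is also tempting to conclude that adding baseline PHQ-9 and GAD-7 to the GEE would be enough. It would not cover drop-out driven by Week 7 scores, and it changes the quantity estimated. On complete data, adding one baseline score (correlation 0.5 to 0.65) moved the log odds ratio from −0.74 to between −0.88 and −1.02, a shift of 19-38% with no drop-out at all. The plan's target is a comparison of rates, which is marginal.

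**What to change.** In 13.5, state for the combined outcome:

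- Missing Week 7 and Week 13 PHQ-9 and GAD-7 scores are multiply imputed by arm from the continuous baseline scores, the available Week 7 scores and the severity stratum.
- The combined variable is derived from the imputed scores, and the GEE is fitted with arm, time and arm by time, with the working correlation named.
- Acceptable alternative: a GEE weighted by the inverse probability of remaining, modelled on baseline and Week 7 scores.
- If baseline PHQ-9 and GAD-7 are added as covariates, standardised (marginal) rates and their difference or odds ratio are reported, because the conditional odds ratio is a different quantity.
- The unweighted GEE on observed visits is kept as a sensitivity analysis.

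No new data are needed; 7.3.4 and 7.4 already call for no missing PHQ-9 or GAD-7 data at screening and baseline. The cost is SAP wording, a little programming, and slightly wider intervals that reflect the missing data.

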### **13.6 Exploratory Objectives, Endpoints, Analysis Plans**

We will perform stratified subgroup analysis of the outcomes in Objectives 1.2.1 and 1.2.2. by gender, age, race/ethnicity, stratification arm (moderate, severe), and psychotropic medication use at baseline to meet Objective 1.3.1 using ANCOVA at week 13. To analyze Objective 1.3.2, we will use a mediation approach to examine whether expectancy ratings mediate the relationship between the intervention and the outcomes of interest (PHQ-9, GAD-7, or the combined outcome) at the intervention mid-point or end. First, we will examine whether the expectancy rating score is a significant predictor of the outcome in the mixed-model analysis of covariance (ANCOVA) model with terms for the expectancy rating score, baseline value of the outcome, therapist or site staff person conducting check-in calls, psychotropic medications use, a time effect (mid-, post-intervention), and the time by intervention expectancy score term (to test whether the expectancy score effects vary by time). Then we will fit the same model with the intervention effect, expectancy rating score, and their interactions with each other and time. If the effect for the mediator is significant in this model and the parameter estimate of the intervention effect is smaller than in the analysis of Objective 1.2.1 it will indicate evidence of mediation.

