### 1.3 Exploratory Objectives

1.3.1. To examine potential differential effects of the intervention on anxiety, depression, sleep disturbance, fatigue, fear of recurrence, and QOL, by gender, age, race/ethnicity, rural v. urban status, stratification arm (moderate, severe), and psychotropic medication use at baseline.

1.3.2. To examine mediating effects of expectancy ratings of the intervention on anxiety and depression.

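### Section 13.6 plans within-subgroup ANCOVAs but no estimate or interval for the difference between subgroups, which is what Objective 1.3.1 asks about

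*Combined protocol and SAP*

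**What the plan says.** Section 1.3 sets the exploratory aim: "To examine potential differential effects of the intervention on anxiety, depression, sleep disturbance, fatigue, fear of recurrence, and QOL", across a list of baseline characteristics. Section 13.6 gives the analysis: "We will perform stratified subgroup analysis of the outcomes in Objectives 1.2.1 and 1.2.2". It names five factors (gender, age, race or ethnicity, severity stratum and baseline psychotropic medication) and specifies ANCOVA at week 13. Nothing else in the document describes how this objective will be analysed.

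Interaction terms are named for two other questions. The section 13.5 model for PHQ-9 and GAD-7 includes "the time by intervention interaction term (to test whether the intervention effects vary by time"). For the mediation objective, section 13.6 says "Then we will fit the same model with the intervention effect, expectancy rating score, and their interactions with each other and time". No intervention-by-subgroup term appears, and there is no rule for interpreting subgroup differences and no multiplicity provision.

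Section 13.8 states that effect analyses serve the planning of later studies and are not meant to show efficacy.

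**The concern.** A differential effect is a difference between two intervention effects. Separate fits give the two effects; the quantity the objective names is left for the reader to construct. Without a stated contrast, the easy reading is to note which subgroups reach significance and which do not. That comparison often suggests a difference where none exists, because each subgroup alone has low power and the two results vary independently.

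The effect analyses are meant to inform a larger trial. A chance contrast between, say, moderate and severe participants could be carried into that trial's design as if it were a finding.

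**Working it through.** **Inputs.** Section 13.3: 36 analysable per arm, "allowing 20% dropout of the 45/group randomized"; SDs of change of 5.8 (PHQ-9) and 4.2 (GAD-7). Section 13.2: 50 moderate and 40 severe participants, allocated 1:1 within stratum. Section 4.3: 15 Hispanic and 75 non-Hispanic participants planned.

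**The plan's own figure.** Half-width = 1.96 × √(2/36) = 0.462 SD, or 2.68 PHQ-9 points and 1.94 GAD-7 points. This matches the stated 0.46 SD, 2.7 and 1.9 points, so the plan's simple two-sample formula is used below.

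**Severity strata after 20% dropout.**
- Moderate: 50/2 × 0.8 = 20 per arm; SE = √(2/20) = 0.316 SD; 95% half-width 0.62 SD.
- Severe: 40/2 × 0.8 = 16 per arm; SE = √(2/16) = 0.354 SD; 95% half-width 0.69 SD.

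**Chance that exactly one stratum is significant when both have the same true effect.** This is pA(1 − pB) + pB(1 − pA), where pA and pB are the two-sided 5% rejection probabilities.

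| Common true effect (SD) | pA (moderate) | pB (severe) | Exactly one significant |
|---|---|---|---|
| 0 | 0.050 | 0.050 | 9.5% |
| 0.30 | 0.158 | 0.136 | 25% |
| 0.46 | 0.307 | 0.256 | 41% |
| 0.66 | 0.551 | 0.463 | 50% |
| 0.80 | 0.716 | 0.619 | 45% |

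At 0.46 SD: 0.307 × 0.744 + 0.256 × 0.693 = 0.406. An interaction test rejects 5% of the time in every row, because a common effect cancels from the contrast. The documents give no expected effect; 0.46 SD is simply the plan's own precision figure, and the other rows show the range.

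**What an interaction estimate would deliver.** SE = √(2/20 + 2/16) = √0.225 = 0.474 SD. The 95% half-width is 1.96 × 0.474 = 0.93 SD, which is 5.4 PHQ-9 points or 3.9 GAD-7 points and about twice the overall 0.46 SD. Power for a true between-stratum difference of 0.46 SD is about 16%; 80% power needs about 1.33 SD.

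**A less balanced factor.** For ethnicity, with an even split by arm assumed, 15 × 0.8/2 = 6 and 75 × 0.8/2 = 30 per arm. The smaller subgroup alone has a half-width of 1.96 × √(2/6) = 1.13 SD. The interaction half-width is 1.96 × √(2/6 + 2/30) = 1.24 SD.

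**Multiplicity.** Five factors in section 13.6 by about seven outcomes is about 35 interaction tests. If they were independent, the chance of at least one false positive would be 1 − 0.95^35 = 83%. The outcomes are correlated, so this is only a guide.

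**The case against.** The strongest reply is that the plan commits to no faulty inference. A reader might infer that effect modification will be declared when one subgroup is significant and another is not. Section 13.6 does not say that: it has a significance-based criterion for mediation but none for subgroups. The 41% is therefore the error of a practice the text leaves open, not of one it adopts. This stands.

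Second, the difference is not out of reach. Subgroups within a factor are disjoint, so two estimates and their standard errors give the contrast by SE = √(SE₁² + SE₂²). This also stands. What is missing is a commitment to report it.

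Third, it is tempting to say that the week 13 restriction throws data away. That could apply only to PHQ-9 and GAD-7; the sleep, fatigue, fear-of-recurrence, distress and quality-of-life measures are not collected at Week 7. The end of the intervention is a sensible single time point, so little of this complaint survives.

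Fourth, stratum-specific estimates are natural for severity, because moderate participants are offered the low-intensity programme and severe participants the high-intensity one. An interaction there mixes severity with the type of intervention. This is right and limits what the severity interaction can mean.

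Fifth, the objective is exploratory in a feasibility study, and no section says that subgroup findings will fix the next trial's population or design. That lowers the importance of the point. It does not make the analysis match its objective.

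**Conclusion.** The concern holds in a limited form. Section 13.6 does not plan to estimate the quantity in Objective 1.3.1, although the same document names interaction terms where it asks whether effects vary with time or expectancy. If significance were compared across the severity strata, equal true effects would give discordant results about 41% of the time at 0.46 SD and between 9.5% and 50% over the effects tabulated, against 5% for an interaction test.

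These figures assume equal variances, dropout of 20% in every subgroup, a normal approximation and no variance reduction from baseline adjustment. A stronger conclusion, that the plan will produce false claims of effect modification at these rates, is not supported, because no such decision rule is stated. No feasibility conclusion and no overall effect estimate changes.

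**What to change.** Amend section 13.6 as follows.

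- For each factor, fit one week 13 model on all randomised participants with an intervention-by-factor term. For PHQ-9 and GAD-7, the Objective 1.2.1 mixed model may be used instead, with the interaction contrast read at week 13.
- Report the interaction estimate with its 95% CI, labelled exploratory, and show subgroup-specific effects as descriptive.
- For severity, state that the interaction mixes severity with intervention intensity (low versus high), and show the stratum-specific estimates alongside it.
- State that no multiplicity adjustment is made and that isolated significant interactions will not be read as established. Settle the factor list at the same time: section 1.3 includes rural versus urban status, while section 13.6 does not.

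The cost is a few sentences of analysis-plan text and no new data. The downside is that the intervals will be visibly wide and multiplicity is disclosed rather than removed. The change guards against over-reading; it does not add power.
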